Official Title: A Phase II, Safety, and Efficacy Study of Tiragolumab Plus Atezolizumab and Atezolizumab Monotherapy in Patients with Metastatic and/or Recurrent PD-L1-Positive Cervical Cancer

NCT04300647 NCT Number:

Document Date: SAP Version 2: 17-June-2021

STATISTICAL ANALYSIS PLAN

TITLE: A PHASE II, SAFETY, AND EFFICACY STUDY OF

TIRAGOLUMAB PLUS ATEZOLIZUMAB AND ATEZOLIZUMAB MONOTHERAPY IN PATIENTS

WITH METASTATIC AND/OR RECURRENT

PD-L1-POSITIVE CERVICAL CANCER

PROTOCOL NUMBER: WO42017

STUDY DRUG: Tiragolumab and Atezolizumab

VERSION NUMBER: 2

IND NUMBER: 147026

EUDRACT NUMBER: 2019-004895-21

SPONSOR: F. Hoffmann-La Roche Ltd

PLAN PREPARED BY:

DATE FINAL: See electronic date stamp below

STATISTICAL ANALYSIS PLAN APPROVAL

Date and Time(UTC) Reason for Signing Name

17-Jun-2021 16:05:04 Company Signatory

CONFIDENTIAL

This is an F. Hoffmann-La Roche Ltd document that contains confidential information. Nothing herein is to be disclosed without written consent from F. Hoffmann-La Roche Ltd.

STATISTICAL ANALYSIS PLAN VERSION HISTORY

SAP Version	Approval Date	Based on Protocol (Version, Approval Date)
2	See electronic date stamp on title page	V 4, 25 March 2021
1	16 December 2020	V 2, 19 June 2020

STATISTICAL ANALYSIS PLAN AMENDMENT RATIONALE

Key changes to the SAP, along with the rationale(s) for each change, are summarized below.

Section	Description of Change	Rationale for Change
4.4.1, 4.1.3, 4.2, 4.3, 4.4	Change of population for efficacy analysis to only randomized patients who receive at least one dose of study treatment. Patients grouped by treatment received.	This change enables evaluation of the efficacy of tiragolumab in combination with atezolizumab and atezolizumab monotherapy in the context of currently available therapy, in line with the use of a prespecified reference for the primary statistical test.
2.3.1	Change of primary analysis timing to enable at least 6 months of follow-up from the onset of response for the majority of patients	This change enables sufficient follow-up of the responders and to assess the durability of the response
2.2.3, 4.4.7	Addition of a potential	This change enables evaluation of consistency with the efficacy and safety observed in the global population

Additional minor changes have been made throughout to improve clarity and consistency.

TABLE OF CONTENTS

ST	ATISTICAL A	NALYSIS PLAN AMENDMENT RATIONALE	3
1.	BACKGRO	UND	7
2.	STUDY DE	SIGN	7
	2.1	Protocol Synopsis	8

This Statistical Analysis Plan (SAP) provides details of the planned analyses and statistical methods for Study WO42017, "A Phase II, Safety, and Efficacy Study of Tiragolumab plus Atezolizumab and Atezolizumab Monotherapy in Patients with Metastatic and/or Recurrent PD-L1–positive Cervical Cancer". The background for the study can be found in the study Protocol.

2. STUDY DESIGN

Study WO42017 is a randomized, Phase II, global, multicenter, open-label study designed to evaluate the efficacy and safety of tiragolumab plus atezolizumab and atezolizumab monotherapy in patients with metastatic and/or recurrent PD-L1-positive cervical cancer after progression or recurrence from at least one platinum-based but no more than two prior systemic therapies.

Approximately 160 patients will be randomized in this study global enrollment phase in a 3:1 ratio. Additional patients may be subsequently randomized in a

. Women with Eastern Cooperative Oncology Group (ECOG) Performance Status of 0 or 1 who have metastatic and/or recurrent PD-L1–positive cervical cancer are eligible (refer to protocol synopsis in Appendix 1 for complete eligibility criterion).

In the doublet arm, patients will receive atezolizumab at a fixed dose of 1200 mg administered by IV infusion Q3W on Day 1 of each 21-day cycle, followed by tiragolumab at a fixed dose of 600 mg administered by IV infusion Q3W also on Day 1 of each 21-day cycle.

In the atezolizumab monotherapy arm, patients will receive atezolizumab at a fixed dose of 1200 mg administered by IV infusion Q3W on Day 1 of each 21-day cycle.

Treatment may be continued as long as patients are experiencing clinical benefit, as assessed by the investigator, in the absence of unacceptable toxicity or symptomatic deterioration attributed to disease progression after an integrated assessment of radiographic data, biopsy results (if available), and clinical status. Patients who meet the criteria for equivocal disease progression per RECIST v1.1 will be permitted to continue treatment (tiragolumab in combination with atezolizumab or atezolizumab alone) if they meet all of the following criteria:

- Evidence of clinical benefit, as assessed by the investigator
- Absence of symptoms and signs (including worsening of laboratory values indicating unequivocal progression of disease)
- No decline in ECOG Performance Status that can be attributed to disease progression

[figure not shown]
 Absence of tumor progression at critical anatomical sites (e.g., leptomeningeal disease) that cannot be managed by protocol-allowed medical interventions

Crossover is allowed from the atezolizumab monotherapy arm to the tiragolumab plus atezolizumab arm after unequivocal progressive disease has been recorded during atezolizumab monotherapy, at the discretion of the investigator and after consultation with the Medical Monitor.

The primary study objectives are to make a preliminary assessment of efficacy of tiragolumab in combination with atezolizumab and atezolizumab monotherapy, as measured by independent review committee (IRC)-determined confirmed objective response rate (ORR), and to evaluate safety.

The study schema is provided in Figure 1.

Figure 1 Study Schema

- Stratification factors:
- ECOG Performance Status (0 vs. 1)
- Prior use of chemoradiotherapy or radiotherapy (yes vs. no)
- Treatment history (persistent vs. recurrent disease)

1L=first-line; CDx=companion diagnostic; ECOG=Eastern Cooperative Oncology Group; PD-L1=programmed death-ligand 1; Q3W=every 3 weeks; R=randomization; s/p= status post.

Note: Crossover is allowed from the atezolizumab monotherapy arm to the tiragolumab plus atezolizumab arm after unequivocal progressive disease has been recorded during atezolizumab monotherapy, at the discretion of the investigator and after consultation with the Medical Monitor.

[figure not shown]
2.1 PROTOCOL SYNOPSIS

The Protocol Synopsis is in Appendix 1. The Protocol Synopsis includes the study objectives, inclusion and exclusion criteria, outcome measures, and statistical methods as stated in the protocol.

2.2	DETERMINATION OF SAMPLE SI	76
Z.Z	DETERMINATION OF SAMPLE SI	

Approximately 160 patients are planned for enrollment in the global enrollment phase. After completion of the global enrollment, additional patients may be subsequently randomized
2.2.1 Type I Error Control
Type I error for the study is (one-sided).
The primary endpoint is confirmed ORR, defined as the proportion of patients with a complete response (CR) or a partial response (PR) on two consecutive occasions ≥4 weeks apart, as determined by an independent review committee (IRC) according to RECIST v1.1.
Primary statistical test is a significance level, and the ORR of the doublet arm will be compared to a historical reference of 14.6% (Chung et al. 2019). This is the only comparison with a statistical hypothesis testing.
No type I error control is applied for descriptive comparisons, including that of the atezolizumab monotherapy ORR to the historical reference.
2.2.2 Primary Endpoint: Confirmed ORR
The overall statistical power under several assumptions of the true underlying ORR in the tiragolumab in combination with atezolizumab arm is given in Table 1, with the following considerations taken into account:
• historical reference of 14.6% (Chung et al. 2019)
• alpha = , one-sided
• 3:1 randomization ratio
True underlying ORR in tiragolumab in combination with atezolizumab arm between

Table 1 Overall Statistical Power in the Comparison of ORR in the Tiragolumab in Combination with Atezolizumab Arm to a Reference Point of 14.6%

[figure not shown]

MDO=minimum detectable observation; ORR=overall response rate.

- ^a Source: Chung et al. 2019.
- b MDO is defined as the smallest observed ORR leading to statistical significance at final analysis.

The ORR in the atezolizumab monotherapy arm will only be compared with the historical reference and with tiragolumab in combination with atezolizumab as a descriptive comparison, with no type I error control. The probability of the observed ORR in the atezolizumab monotherapy arm being greater than a reference point at the time of final ORR analysis is also shown in Table 2.

Table 2 Probability of Observed ORR in the Atezolizumab Monotherapy
Arm Greater than a Reference Point at the Final Analysis for ORR

ORR = overall response rate.

^a Source: Chung et al. 2019.

2.3 INTERIM AND PRIMARY ANALYSIS TIMING

2.3.1 **Primary Analysis Timing**

The analysis of confirmed ORR for

The primary analysis of confirmed ORR will be performed once all patients have been enrolled and a minimum follow-up of approximately 6 months after the second tumor assessment, or approximately 9 months after randomization, has been achieved among the patients, who remain in follow-up for ORR assessment, whichever is earlier.

will be conducted after all

enrolled Chinese patients have had a minimum follow-up of approximately 6 months after the second tumor assessment, or approximately 9 months after randomization, has been achieved among the patients, who remain in follow-up for ORR assessment, whichever is earlier.

3. STUDY CONDUCT

3.1 RANDOMIZATION ISSUES

Eligible patients will be randomized in a 3:1 ratio to receive either atezolizumab plus tiragolumab or atezolizumab monotherapy with the use of a stratified permuted-block randomization. The randomization will be stratified for the following factors:

- ECOG Performance Status (0 vs. 1)
- Prior use of chemoradiotherapy or radiotherapy (yes vs. no)
- Treatment history (persistent vs. recurrent disease)

3.2 INDEPENDENT REVIEW COMMITEE

An Independent Review Committee (IRC) will be used to conduct a blinded radiology review of the imaging data and will provide an independent assessment of tumor response and progression for all patients according to a separate IRC Charter. The IRC will follow the Response Evaluation Criteria in Solid Tumor, Version 1.1 (RECIST 1.1).

3.3 DATA MONITORING

The Sponsor will monitor patient safety throughout the study. In addition to the ongoing assessment of the incidence, nature, and severity of adverse events; deaths; vital signs; and laboratory abnormalities, the Sponsor will review all cumulative data at regular intervals during the study.

An Internal Monitoring Committee (IMC) composed of representatives from safety science, clinical science, and statistics, who are independent from the study team, will also be established. Representatives from other functions may be added on an ad hoc

basis depending on the nature of the findings. The primary responsibility of the IMC is to evaluate the safety, not efficacy, of treatment arms being evaluated. The IMC will share responsibility with the study team for the monitoring of patient safety.

The IMC may meet during the course of the study. The IMC may conduct an ad hoc meeting should an unexpected safety concern arise, as specified in the IMC Charter. At the time of each review of cumulative data, the IMC may make recommendations in consideration of the totality of the available data. Specific operational details such as the committee's composition, timing of meetings, and members' roles and responsibilities will be detailed in an IMC Charter.

4. STATISTICAL METHODS

The analyses described in this SAP will supersede those specified in Protocol WO42017 for the purposes of a regulatory filing.

4.1 ANALYSIS POPULATIONS

4.1.1 Treated Patients Population

The Treated Patients Population is defined as all randomized patients that have received at least any dose of study treatment. Patients will be grouped according to the actual treatment received. The Treated Patients Population will be used at primary analysis for the efficacy analysis.

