4.1.3 IA Treated Patients Population

The IA Treated Patients Population is defined as all patients randomized at least 5 months prior to the interim analysis CCOD that have received at least any dose of study treatment. Analysis by treatment arm performed on the IA Treated Patients Population will be grouped according to the actual treatment received. The IA Treated Patients Population will be used at interim analysis for the efficacy analysis.

4.1.4 Crossover Population

The Crossover Patients, Treated Patients Population or Safety Population is defined as all patients randomized to the atezolizumab monotherapy arm that crossed-over to the tiragolumab in combination with atezolizumab arm, and received at least any dose of tiragolumab after cross-over but not prior to cross-over.

4.1.5 Pharmacokinetic-Evaluable Population

The Pharmacokinetic-Evaluable Population is defined as all patients who received any dose of study treatment and who have at least one post-baseline PK sample available.

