4.1.6 Safety Population

The safety population is defined as patients who received at least one dose of tiragolumab or atezolizumab. The Safety Population is identical to the Treated Patients Population (see Section 4.1.1) and will be used for the safety analysis.

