4.6 SAFETY ANALYSES

Unless specified otherwise, safety analyses described below will be conducted for the Safety Population (see Section 4.1.3).

Patients will be grouped into two categories:

- atezolizumab monotherapy
 - Patients that received at least one dose of atezolizumab and never received any dose of tiragolumab.
 - Information from patients originally randomized to atezolizumab monotherapy; that received at least one dose of atezolizumab prior to crossover and received a dose of tiragolumab after crossover; safety information up until the first dose of tiragolumab treatment will be included.
- tiragolumab in combination with atezolizumab
 - Patients originally randomized to tiragolumab in combination with atezolizumab that received at least one dose of tiragolumab.
 - Patients randomized to atezolizumab monotherapy that received a dose of tiragolumab (due to a medication error) prior to an eventual crossover.

Information after the start of tiragolumab, for patients randomized to atezolizumab that received a dose of tiragolumab after crossover, will be reported in separate safety analysis. Only selected safety analysis will be performed on this Crossover Patients, Safety Population.

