Administration of tiragolumab and atezolizumab will be performed in a monitored setting where there is immediate access to trained personnel and adequate equipment and medicine to manage potentially serious reactions.

Statistical Methods

Primary Analysis

The primary efficacy objective for this study is to evaluate the efficacy of tiragolumab in combination with atezolizumab and of atezolizumab monotherapy on the basis of the following endpoint:

ORR, defined as the proportion of patients with a CR or PR on two consecutive occasions
 ≥4 weeks apart, as determined by the IRC according to RECIST v1.1

The primary efficacy analysis population will consist of all randomized patients who receive at least one dose of study treatment, with patients grouped according to treatment received.

[figure not shown]
The primary efficacy analysis will take place once all patients have been enrolled and a minimum follow-up of approximately 6 months after the second tumor assessment, or approximately 9 months after randomization, has been achieved among those patients, who remain in follow-up for ORR assessment, whichever is earlier.

In the primary analysis, patients whose ORR assessment was missing will be counted as not achieving a response. A one-sample z-test for proportion will be used for comparing the ORR of the tiragolumab in combination with atezolizumab arm to the historical reference. An estimate of the ORR and its 95% CI will be calculated for each treatment arm.

Determination of Sample Size

A total of 160 patients will be enrolled in this study and randomized in a 3:1 ratio (tiragolumab in combination with atezolizumab and atezolizumab monotherapy). The overall statistical power for several assumptions of the true underlying ORR in tiragolumab in combination with atezolizumab arm takes the following considerations into account:

• Primary statistical test is a significance level, and the doublet arm will be compared to a historical reference of 14.6%.

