- ^g Vital signs include respiratory rate, pulse rate, systolic and diastolic blood pressure, and temperature. Vital signs should be recorded as described in Section 4.5.4 of the protocol.
- h Complete physical examination must include pelvic examination. Limited physical examination will be a symptom-directed physical examination, as clinically indicated; see Section 4.5.3 of the protocol for details.
- ECGs for each patient should be obtained from the same machine wherever possible. Lead placement should be as consistent as possible. ECG recordings must be performed after the patient has been resting in a supine position for at least 10 minutes.
- Hematology consists of WBC count, hemoglobin, platelet count, and differential count (neutrophils, eosinophils, basophils, monocytes, and lymphocytes).
- ^k Chemistry panel (serum or plasma) includes sodium, potassium, glucose, BUN or urea, creatinine, albumin, total calcium, total and direct bilirubin, ALP, ALT, AST, and LDH.

- Pregnancy test should be performed for women of childbearing-potential only. Pregnancy test (serum or urine) must be performed ≤14 days prior to Cycle 1, Day 1. A positive urine pregnancy test must be confirmed by a quantitative serum pregnancy test and an ultrasound confirming intrauterine pregnancy.
- ^m TSH, free T3 (or total T3 for sites where free T3 is not performed), and free T4 will be assessed on Day 1 of Cycles 1, 5, 9, and 13, and every fourth cycle thereafter. The thyroid-function test in Cycle 1 does not need to be performed if the previous test was performed within the screening window.

1	
	i

- Urinalysis is required at screening and can be by dipstick (glucose, protein, ketones, blood, leukocyte esterase, nitrites, WBC, bacteria, and epithelial cells).
- P The initial cycle of atezolizumab plus tiragolumab or atezolizumab monotherapy should be administered over minutes for each agent. Subsequent infusions of each agent should be infused over minutes if the previous infusion was tolerated without an infusion-related reaction, or minutes if patient experienced an infusion-related reaction with the previous infusion (see Section 4.3.2 of the protocol). For the tiragolumab and atezolizumab doublet, the tiragolumab must be administered after the atezolizumab.

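### Does grouping the efficacy population by treatment received, without a stated class for partly dosed patients, undermine the test against 14.6%?

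*SAP*

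**What the plan says.** The SAP states the same rule in three places. For the primary analysis, section 4.1.1 takes randomised patients with any dose of study treatment and adds: "Patients will be grouped according to the actual treatment received". For the interim analysis, section 4.1.3 says: "Analysis by treatment arm performed on the IA Treated Patients Population will be grouped according to the actual treatment received". The synopsis in Appendix 1, under Primary Analysis, describes the population "with patients grouped according to treatment received". The amendment rationale lists the change and gives its reason: to evaluate each regimen in the context of available therapy, in line with a primary test against a prespecified reference.

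The detailed classes are in section 4.6. Monotherapy includes "Patients that received at least one dose of atezolizumab and never received any dose of tiragolumab". The combination includes "Patients originally randomized to tiragolumab in combination with atezolizumab that received at least one dose of tiragolumab" and also "Patients randomized to atezolizumab monotherapy that received a dose of tiragolumab (due to a medication error) prior to an eventual crossover". Section 4.1.6 ties this to efficacy: "The Safety Population is identical to the Treated Patients Population (see Section 4.1.1"). Section 4.1.4 gives a single definition of crossover patients for both the Treated and the Safety populations, and leaves out anyone given tiragolumab before crossover.

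Sections 2.2.1 and 4.4.1.1 confine formal testing to the combination arm against 14.6%. Sections 4.1.2 and 4.4.5 plan a confirmed response rate in the ITT Population, grouped by assignment.

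**The concern.** In a randomised, open-label trial, statisticians expect efficacy to be analysed as randomised, because what a patient receives after randomisation can depend on how she is doing. Here the tested denominator depends on dosing. Appendix 2, footnote p, says that "the tiragolumab must be administered after the atezolizumab". A patient assigned to the combination can therefore receive atezolizumab, run into trouble, and never receive tiragolumab. She is treated, so she stays in the population. If she is classed by what she received, she leaves the arm being tested. Such patients may well be non-responders, and removing them would raise the combination response rate. A monotherapy patient given tiragolumab by mistake would move the other way.

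The efficacy sections do not spell out either case; the explicit rules stand under safety. If the class were left open until responses were known, the one confirmatory result could depend on a late decision. That would matter if the patients were many or the result close.

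**Working it through.** **Which rule applies**

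| Patient | Section 4.6 class | Support on the efficacy side |
|---|---|---|
| Randomised to combination, atezolizumab only | Monotherapy | Sections 4.1.1 and 4.1.3 group by treatment received, and she received atezolizumab alone; section 4.1.6 equates the two populations |
| Randomised to monotherapy, tiragolumab by error before crossover | Combination | Section 4.1.4 leaves her out of the crossover set, for the Treated and Safety populations together |
| Randomised to monotherapy, tiragolumab only after crossover | Monotherapy up to the first tiragolumab dose | Section 4.4.4.1 analyses response after crossover separately |

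The efficacy sections do not repeat the rule, but nothing in them conflicts with it.

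**Inputs**

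- About 160 patients at 3:1 (section 2): 160 × 3/4 = 120 combination and 40 monotherapy, all assumed treated.
- Reference 14.6%, one-sample z-test (sections 2.2.1 and 4.4.1.1).
- Alpha is blacked out, so one-sided values from 0.01 to 0.10 are assumed. The power table is not readable, so there is no stated power figure to reproduce.
- 24 responders in the combination arm and 8 in monotherapy are assumed for illustration.

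**Effect on the estimate**

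- Nobody moved: 24/120 = 20.0%.
- One combination non-responder moved out: 24/119 = 20.2%, about +0.2 points.
- One monotherapy non-responder moved in: 24/121 = 19.8%, about −0.2 points.
- One of each: 24/120 = 20.0%.
- The patient moved out joins monotherapy: 8/40 = 20.0% becomes 8/41 = 19.5%, which enters descriptive results only.

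**Effect on the test**

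z = (x/n − 0.146) / √(0.146 × 0.854 / n)

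At an assumed alpha of 0.025 (critical value 1.960), 26 responders of 120 are needed, or 25 of 119. With 25 responders:

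- n = 120: (0.2083 − 0.146)/0.03223 = 1.93, not significant.
- n = 119: (0.2101 − 0.146)/0.03237 = 1.98, significant.

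So one patient can tip the result, but only at an exact boundary. Among arm sizes 106 to 135 at alpha 0.025, the required count changes with one patient at 5 of 30 sizes (109, 114, 120, 126, 131), and 120 is one of them. The sizes differ for other values of alpha.

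**Effect on the false-positive chance (n = 120, alpha 0.025, exact binomial)**

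1. Nobody moved, 120 tested, cut-off 26: X ~ Bin(120, 0.146) gives 2.37%.
2. 119 tested at a true rate of 14.6%, cut-off 25: X ~ Bin(119, 0.146) gives 3.68%.
3. One certain non-responder moved out, with 14.6% held as the true rate among all 120: the rate in the 119 is 0.146 × 120/119 = 14.72%, and X ~ Bin(119, 0.1472) gives 4.01%.

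The step from 1 to 2 is the discreteness of the z-test at a different sample size; a trial that simply enrolled 119 would show it. Only the step from 2 to 3, 0.33 points, comes from regrouping. It exists because the calculation fixes 14.6% in the patients as randomised. If 14.6% is the true rate in patients who received tiragolumab, line 2 applies and regrouping adds nothing.

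Averaged over sizes 106 to 135, the same conditional difference is 0.15, 0.28, 0.45 and 0.73 points at alpha 0.01, 0.025, 0.05 and 0.10.

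**The case for a change.** The strongest case for the concern has three parts.

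First, the stated reason for the amendment supports restricting the analysis to treated patients but does not force moving treated patients between arms; analysing them in their randomised arm was possible. That is true, but it shows only that there was another option. The plan aims to evaluate the combination against an external rate, and a patient who never received tiragolumab was not given the combination. No comparison between arms is tested, so the main argument for keeping patients as randomised has little force. Dependence of the denominator on dosing is also not peculiar to regrouping, because any population of treated patients drops those never dosed.

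Second, section 4.1.1 does not itself classify partly dosed patients, and applying the section 4.6 rule to response is an inference. This stands as an observation: a cross-reference from 4.1.1 to 4.6 would be tidier. The inference is short and well supported, however, and the plan offers no competing rule.

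Third, the ITT estimate adds never-dosed patients as well as restoring assignment, and it carries no test, so it does not isolate the effect of regrouping. That is also correct. It would still show whether the result depends materially on the choice of population, which is what a sensitivity analysis is for.

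**Conclusion.** The concern does not hold. Grouping by treatment received is stated consistently, disclosed and given a reason, and it suits a single-arm test against a fixed 14.6%. Preferring the randomised arm here is a matter on which reasonable statisticians differ. The missing restatement in section 4.1.1 is a detail that sections 4.6, 4.1.6 and 4.1.4 together supply, so an analyst following the plan would class these patients sensibly.

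The size is about 0.2 percentage points of response rate per patient moved, in either direction, with opposite moves cancelling. This assumes 120 treated combination patients and 24 responders. The false-positive increments of 0.15 to 0.73 points rest on an assumed alpha, an assumed non-responder and a true rate of 14.6% defined in patients as randomised; they vanish if that rate is defined in patients given the combination. How many patients would be affected is not known, but the number is probably very small. If there are none, nothing changes.
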